6.1.6 Laboratory Evaluations

The following laboratory parameters will be examined according to the Schedules of Evaluations and Procedures as outlined in [Table 6-1](#) and [Table 6-2](#) ([Table 6-3](#) and [Table 6-4](#) for the standard of care group). While not all abnormal laboratory results would be considered

clinically significant as determined by the investigator (ie, those that are associated with the disease state and were present at baseline), those that are determined to be a clinically significant change (ie, worsening) from baseline or known medical history will be considered adverse events. All such abnormal laboratory values that are considered AEs must be recorded on the appropriate eCRF. A result outside of the normal range may be repeated for confirmation. Any laboratory test result that meets the criteria for an SAE (Section 6.1.2) must also be recorded in an SAE report so that the sponsor/designee can collect additional information about that abnormality, including information regarding relationship to investigational product or other causes, any action taken, and outcome.

Laboratory collections that are required at intervals that do not coincide with clinic visits (ie, for safety lab assessments done following PN/IV adjustments) may be obtained by a Home Health Agency at subjects' homes.

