7.2. BASELINE

Unless otherwise specified, baseline is defined as the last non-missing measurement taken prior to or on the reference start date (including unscheduled assessments). For adverse events (AE) or concomitant medications that start on the reference start date, the time of onset will be compared to the time of the first dose of study drug to determine if the AE or medication was pre-baseline or post-baseline. If the timing relative to the first dose of study drug is unknown, AEs and medications commencing on the reference start date will be considered post-baseline. Actual PN/IV and EN administration on the day of the reference start will be considered post-baseline.

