19.1. ADVERSE EVENTS

Adverse Events (AEs) will be coded using *Medical Dictionary for Regulatory Activities (MedDRA) central coding dictionary, Version 19.1*. Investigator verbatim as well as preferred terms and system organ classes will be included in the listings.

Treatment-emergent adverse events (TEAEs) are defined as AEs that started or worsened on or after the date of first dose for treatment arms and adverse events that started or worsened on or after the baseline visit for standard of care group. For events that start or worsen on the date of

Document:	\\quintiles.net\Enterprise\Apps\sasdata\SASa\sas\Shire\Teduglutide\Biostatistics\Documentation\SAP\TE D-C14-006_SAP_Final_V1.0_20170714		
Author:	PPD	Version Number:	Final V1.0
		Version Date:	14Jul2017
Template No:	CS_TP_BS016 – Revision 3	Reference:	CS_WI_BS005
Effective Date:	01May2012		

first dose, any available start time will be compared to the time of first dose for the treatment arms.

See [Appendix 2](#) for handling of partial dates for AEs. In the case where it is not possible to define an AE as treatment-emergent or not, the AE will be classified by the worst case; i.e. treatment-emergent.

An overall summary of number of subjects within each of the categories described below will be provided as specified in the templates. Adverse events will be summarized using descriptive statistics (e.g., number and percentage of subjects) for each treatment arm and dose group. The number of events will also be presented except for summaries by highest category. The summary will include any TEAE, severity of TEAEs (highest category), investigator assessment of relationship of TEAEs to study drug, treatment-emergent serious AEs (TESAEs), investigator assessment of relationship of TESAEs to study drug, TEAEs leading to discontinuation and TEAEs leading to death.

Listings will include both TEAEs and Non-TEAEs (unless specified otherwise) and will be provided for serious adverse events, adverse events leading to death, and adverse events leading to discontinuation of study drug. Listings will indicate whether an AE is treatment emergent or not.

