Quantitative laboratory measurements reported as “< X”, i.e. below the lower limit of quantification (BLQ), or “> X”, i.e. above the upper limit of quantification (ULQ), will be converted to X for the purpose of quantitative summaries, but will be presented as recorded, i.e. as “< X” or “> X” in the listings.

The following summaries will be provided for hematology, clinical chemistry and selected urinalysis laboratory data with quantitative results:

Document:	\\quintiles.net\Enterprise\Apps\sasdata\SASa\sas\Shire\Teduglutide\Biostatistics\Documentation\SAP\TE D-C14-006_SAP_Final_V1.0_20170714		
Author:	PPD	Version Number:	Final V1.0
		Version Date:	14Jul2017

Template No: CS_TP_BS016 – Revision 3
Effective Date: 01May2012

Reference: CS_WI_BS005

Copyright © 2012 Quintiles Transnational Corp. All rights reserved.

The contents of this document are confidential and proprietary to Quintiles Transnational Corp. Unauthorized use, disclosure or reproduction is strictly prohibited.

- Actual and change from baseline by scheduled site visit
- Shift from baseline according to normal range criteria at each scheduled post-baseline site visit
- Incidence of markedly abnormal values according to criteria defined in section Appendix 3
- Listing of subjects meeting markedly abnormal criteria

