19.2.1. LABORATORY REFERENCE RANGES AND MARKEDLY ABNORMAL CRITERIA

Quantitative laboratory measurements will be compared with the relevant laboratory reference ranges in SI units and categorized as:

- Low: Below the lower limit of the laboratory reference range.
- Normal: Within the laboratory reference range (upper and lower limit inclusive).
- High: Above the upper limit of the laboratory reference range.

In addition to the high and low quantitative laboratory assignments (as identified by means of the laboratory reference ranges), markedly abnormal quantitative safety (and other) laboratory assessments will also be identified in accordance with the predefined markedly abnormal criteria as presented in [Appendix 3](#).

The number and percentage of subjects whose post-baseline results qualifying as markedly abnormal will be summarized by treatment group and the parameter. A listing will present all values for a subject and laboratory parameter if at least one post-baseline value for that subject and parameter is markedly abnormal.

Laboratory results will also be included in appendix data listings for each lab panel (chemistry, hematology, coagulation and urinalysis) by treatment, subject, visit and parameter. Values outside the normal range will be flagged. Local lab test results will only be presented in appendix data listings. Categorical test results, coagulation and pregnancy results (B-hCG, Qualitative and B-hCG, Quantitative) also will only be included in data listings.

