APPENDIX 1. PROGRAMMING CONVENTIONS FOR OUTPUTS

SHIRE OUTPUT STANDARDS – TFLs4SHIREFINALV6.0

Outputs will be presented according to Shire output standards document TFLs4ShireFinalV6.0. General considerations which are applicable to the study are summarized as following:

- **STATISTICS PRESENTATION**

For the by-time-point tables, the number of subjects at each timepoint (n) represents the number that had a valid result for a given parameter at that timepoint.

The default summary statistics presented in the TFLs4Shire table shells for continuous variables include n, mean, standard deviation, median, minimum, and maximum. For categorical variables, the count (n) and percent (%) are the default statistics; unless otherwise stated or the associated number of subjects for the corresponding time point is provided, the denominator for percentages is N (the number of subjects in the treatment group/analysis set). Note that for any summary by subgroups (e.g., by sex), the denominator is the number of subjects in that subgroup/treatment group/analysis set. For most safety tables the study teams should use the default statistics; the study team should carefully consider and give sufficient justification prior to requesting the use of other summary statistics. Percentages will be reported to 1 decimal place, except when the percentage equals exactly 100 where it will be displayed as an integer (100). For zero, only count and no percentage will be displayed.

- **ALIGNMENT**

Output should be aligned so that in the body of the table, where applicable, text is left-justified within a cell, stats output is aligned centrally within a cell and lined up by decimal point.

Handling of missing values: In listings, missing values for numerical data will be reported as a period “.” and missing values for character data as a blank “ ”. In the summary tables for categorical data, “Missing” will always be displayed as a category to represent missing data, where applicable. The default denominator will be all subjects in the analysis set unless otherwise specified in the SAP. For both tables and listings where there are no observations (and hence there would be no output), the table/listing should be produced with all titles and footnotes as per its shell, but with the text showing no observations in the body of the output.

Document:	\\quintiles.net\Enterprise\Apps\sasdata\SASa\sas\Shire\Teduglutide\Biostatistics\Documentation\SAP\TE D-C14-006_SAP_Final_V1.0_20170714		

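### The planned incidence of markedly abnormal laboratory values ignores baseline, so a persistent pre-existing abnormality counts as an on-study case for that dose

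*SAP*

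**What the plan says.** SAP 19.2 lists among the laboratory outputs "Incidence of markedly abnormal values according to criteria defined in section Appendix 3". SAP 19.2.1 gives the counting rule: "The number and percentage of subjects whose post-baseline results qualifying as markedly abnormal will be summarized by treatment group and the parameter". The supporting listing prints all of a child's values for a parameter "if at least one post-baseline value for that subject and parameter is markedly abnormal".

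Under the output conventions in SAP Appendix 1, unless something else is stated, "the denominator for percentages is N (the number of subjects in the treatment group/analysis set").

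The other summaries of quantitative laboratory results in SAP 19.2 are actual values and change from baseline by visit, and "Shift from baseline according to normal range criteria at each scheduled post-baseline site visit". SAP 7.2 supplies a usable baseline: "baseline is defined as the last non-missing measurement taken prior to or on the reference start date".

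Elsewhere the plan does condition on baseline. SAP 19.1 states: "Treatment-emergent adverse events (TEAEs) are defined as AEs that started or worsened on or after the date of first dose". Protocol 6.1.6 separates clinically significant worsening from abnormal results that are not clinically significant, which it describes as "those that are associated with the disease state and were present at baseline".

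**The concern.** An incidence is normally read as new occurrence among those at risk. Here the numerator admits children whose abnormality predates the drug, and the default denominator includes children who cannot become new cases for that parameter.

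The Protocol (1.2 and 1.3) describes these children as dependent on parenteral support, at risk of liver disease and with biliary comorbidity, so abnormal entry values on some tests are plausible. Safety is part of the stated objective (Protocol 2.1, SAP 3). With about 10 children per dose arm, one or two pre-existing abnormalities that fall unevenly could look like a laboratory signal for one dose. The standard of care group is chosen by the family rather than randomized (Protocol 5.2, SAP 4.1), so its baseline mix may also differ for reasons other than chance.

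**Working it through.** The plan gives no figure for this point, so there is none to reproduce.

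**1. Is there a baseline condition anywhere?** SAP 7.2, 19.2, 19.2.1 and Appendices 1 and 3 contain none for this table: no requirement that the baseline be below the cut-off, none for worsening, and no restricted denominator.

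**2. Does another summary supply it?** Take a child with alkaline phosphatase above 5 x ULN throughout, and another who moves from mildly raised to above 5 x ULN. Both appear as high to high in the shift table, and both count once in the markedly abnormal table. Change from baseline is a group summary and does not identify children. Only the listing separates the two.

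**3. Which parameters are open at entry?** Appendix 3 has 18 chemistry + 5 hematology = 23 parameters. Compared with Protocol 4.3:

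| Parameter | Excluded at entry | Markedly abnormal |
|---|---|---|
| ALT | ≥ 7 x ULN | > 8 x ULN |
| AST | ≥ 7 x ULN | > 8 x ULN |
| Total bilirubin | ≥ 2 x ULN | > 3 x ULN |
| Creatinine | indirectly, eGFR < 50 mL/min/1.73 m² | age-specific limits |
| Direct bilirubin | indirectly, through total | > 34.208 umol/L |

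Direct bilirubin cannot exceed total. Total must be below 2 x ULN, so a direct value above 34.208 at entry needs 2 x ULN > 34.208, that is, a total bilirubin ULN above 34.208 / 2 = 17.1 umol/L. The documents do not give the ULN. Setting these five aside leaves 23 − 5 = 18 parameters with no numeric entry limit, among them alkaline phosphatase, platelets, hemoglobin, triglycerides and BUN.

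**4. Effect per child.** Let n = 10 (the minimum per dose arm, Protocol 4.1), b = children markedly abnormal at baseline who remain so, and m = new cases. The SAP figure is (b + m)/n. The new-onset figure is m/(n − b).

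| b | m | SAP figure | New-onset figure |
|---|---|---|---|
| 1 | 0 | 1/10 = 10% | 0/9 = 0% |
| 2 | 0 | 2/10 = 20% | 0/8 = 0% |
| 2 | 1 | 3/10 = 30% | 1/8 = 12.5% |
| 3 | 1 | 4/10 = 40% | 1/7 = 14.3% |

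In a standard of care group of 8, one child is 1/8 = 12.5 points.

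**5. Chance imbalance (illustration only).** Assume a baseline prevalence p of marked abnormality on one parameter, equal in both dose arms, with persistence, independent children and no drug effect. P(at least one in an arm) = 1 − (1 − p)^10. The probability that the arms differ by two or more children comes from two independent binomials with n = 10.

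| p (assumed) | At least one in an arm | Arms differ by ≥ 2 children (20 points) |
|---|---|---|
| 5% | 40% | 11% |
| 10% | 65% | 24% |
| 20% | 89% | 39% |

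**6. Intermittent abnormalities.** There are 12 post-baseline site visits with central laboratory tests (Weeks 1, 2, 4, 6, 8, 10, 12, 15, 18, 21, 24, 28), and one hit is enough. If a chronic abnormality shows at a fraction q of visits, independently, it is flagged with probability 1 − (1 − q)^12: 72% for q = 10% and 97% for q = 25%. Both values of q are assumptions.

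**The case against.** The strongest reply is that this is a matter of presentation. For every counted child the listing shows all values of that parameter, baseline included, and with about 10 per arm it can be read by eye. No between-group comparison of safety data is planned (SAP 19) and no significance will be claimed (SAP 7.5). Clinically significant worsening also reaches the adverse event tables. This stands so far as it goes: no data are lost and no test is biased. But the count and percentage by dose remain, under a label that implies new onset, and the reader would have to correct them by hand.

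A reader might infer that all the parameters without an entry limit will carry chronic marked abnormalities. The documents do not support that. Many cut-offs are extreme (potassium < 2.5 or > 6.5 mmol/L, sodium < 120 or > 160 mmol/L, hemoglobin < 70 g/L), and nothing shows that such values persist. Stable parenteral support and the exclusions for recent major admissions and unstable disease narrow the pool further.

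An all-comers count is also conservative, and dropping baseline-abnormal children would hide further worsening, for example alkaline phosphatase rising from 5.5 to 15 x ULN. That is a sound argument for keeping the present count beside a new one.

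Finally, the table shells are in a separate file and might add a baseline row or a different denominator. The SAP is based on protocol amendment 4, whereas the history in the protocol supplied ends at amendment 2, so the governing entry limits may differ. Neither point puts a baseline condition into the SAP text.

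**Conclusion.** The point holds as a defect in the label and the count. As written, the table mixes pre-existing and new marked abnormality, and no planned summary table separates them. Each persistent baseline abnormality adds 10 points in a 10-child arm for that parameter. The total effect cannot be sized, because the documents give no baseline frequency; the probabilities above rest on assumed prevalences, persistence and independence.

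It would be too strong to say that the table will read as a dose effect. It could be misread that way, but no comparison is planned and the listing allows the reader to check. The count of 18 parameters means only that no numeric entry limit exists in the protocol supplied, not that children will enter abnormal on them.

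**What to change.** In SAP 19.2 and 19.2.1, relabel the existing count as any post-baseline markedly abnormal value. Beside it add, for each parameter and direction:

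- the number of children markedly abnormal at baseline;
- a treatment-emergent count. The numerator is children with a post-baseline markedly abnormal value whose baseline was not markedly abnormal in the same direction. The denominator is children with such a non-missing baseline and at least one post-baseline value.

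Direction needs stating because 11 of the 23 parameters have both a lower and an upper cut-off. Keep the full-value listing, so that worsening in children already abnormal at baseline stays visible. If the shells already contain a baseline row, bring the SAP text into line with them.

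The cost is a sentence or two in the SAP, a baseline condition in the program, and one or two extra rows per parameter. No new data are needed. One limit remains: a single-value baseline will not remove intermittent chronic abnormalities. Using the screening value as well to classify baseline status would help with these.

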2. INTRODUCTION

This document describes the rules and conventions to be used in the presentation and analysis of efficacy and safety data for Protocol TED-C14-006. It describes the data to be summarized and analyzed, including specifics of the statistical analyses to be performed. Pharmacokinetic (PK) concentration will be summarized but the analysis of PK parameters will be detailed in a separate analysis plan.

This statistical analysis plan (SAP) is based on protocol amendment 4, dated 15 March 2016.

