7.3. RETESTS, UNSCHEDULED VISITS AND EARLY TERMINATION DATA

In general, for by-visit summaries, data recorded at the nominal visit will be presented. Unscheduled measurements will not be included in by-visit summaries, but can contribute to

Document:	\\quintiles.net\Enterprise\Apps\sasdata\SASa\sas\Shire\Teduglutide\Biostatistics\Documentation\SAP\TE D-C14-006_SAP_Final_V1.0_20170714		
Author:	PPD	Version Number:	Final V1.0
		Version Date:	14Jul2017

Template No: CS_TP_BS016 – Revision 3
Effective Date: 01May2012

Reference: CS_WI_BS005

Copyright © 2012 Quintiles Transnational Corp. All rights reserved.

The contents of this document are confidential and proprietary to Quintiles Transnational Corp. Unauthorized use, disclosure or reproduction is strictly prohibited.

the EOS/EOT value, or best/worst case value where applicable. Unscheduled PN/IV or EN prescription adjustments carry forward until the net adjustment, and as such, may contribute to data assigned to subsequent visits.

Listings will include scheduled, unscheduled, retest and early discontinuation data.

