8.3. MISSING DATA

Missing data will in general not be imputed. However, partial dates will contribute to analyses as described in [Appendix 2](#). All available data will be included in the safety analysis.

Details for the imputation algorithm for the missing endpoint values for PN/IV support parameters (volume, calories and etc.) will be described in Section [17.1.1](#) of this analysis plan.

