19.2. LABORATORY EVALUATIONS

Laboratory evaluations that are done at study site visits will be collected and processed via a central laboratory (Covance), including panels for Hematology, Clinical Chemistry, Coagulation and Urinalysis. The central laboratory data will be transferred to Quintiles for analyses. Laboratory evaluations that are required at intervals that do not coincide with study site visits may be obtained by a local laboratory. The local laboratory data will be collected on the local laboratory tests form of eCRF. Laboratory evaluations to be included in the tables or listings are presented in the lab test table ([Table B](#)) below.

Document:	\\quintiles.net\Enterprise\Apps\sasdata\SASa\sas\Shire\Teduglutide\Biostatistics\Documentation\SAP\TE D-C14-006_SAP_Final_V1.0_20170714		
Author:	PPD	Version Number:	Final V1.0
		Version Date:	14Jul2017

Template No: CS_TP_BS016 – Revision 3
Effective Date: 01May2012

Reference: CS_WI_BS005

Copyright © 2012 Quintiles Transnational Corp. All rights reserved.

The contents of this document are confidential and proprietary to Quintiles Transnational Corp. Unauthorized use, disclosure or reproduction is strictly prohibited.

Table B Laboratory Tests

Hematology	Chemistry	Coagulation	Urinalysis
Hemoglobin	Albumin	Prothrombin Time	Ur Blood*
Hematocrit	Alkaline Phosphatase	Prothrombin Intl. Normalized Ratio (INR)	Ur Glucose*
Platelets	Alanine Aminotransferase (ALT)		Ur Microscopic*
Erythrocytes	Aspartate Aminotransferase (AST)		Ur PH
RBC Morphology*	Amylase		Ur Osmolality
Leukocytes	Lipase		Ur Protein
Neutrophils	Bicarbonate		Ur Sodium
Lymphocytes	Bilirubin		Ur Specific Gravity
Monocytes	Direct Bilirubin		
Eosinophils	Indirect Bilirubin		
Basophils	Blood Urea Nitrogen		
Neutrophils/Leukocytes	Calcium		
Lymphocytes/Leukocytes	Chloride		
Monocytes/Leukocytes	Cholesterol		
Eosinophils/Leukocytes	Creatinine		
Basophils/Leukocytes	C Reactive Protein		
	Glomerular Filtration Rate (GFR)		
	Glucose		
	Gamma Glutamyl Transferase (GGT)		
	Lipase		
	Magnesium		
	Phosphorus		
	Potassium		
	Sodium		
	Triglycerides		
	Uric Acid		

Note: * lab tests with categorical results.

Lab data will be presented in SI units. The summaries will be based on central lab results only.

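### The markedly abnormal laboratory incidence table counts central-laboratory results only, so a subject whose only qualifying value for a parameter came from a local laboratory is not counted (size unknown, possibly zero)

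*SAP*

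**What the plan says.** SAP 19.2 sends samples taken at site visits to a central laboratory. For other samples it says: "Laboratory evaluations that are required at intervals that do not coincide with study site visits may be obtained by a local laboratory". The local results are entered on their own eCRF form, so they are in the database.

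The same section then sets the source rule: "The summaries will be based on central lab results only". The list of summaries that follows has, as separate items, "Incidence of markedly abnormal values according to criteria defined in section Appendix 3" and a listing of the subjects who meet those criteria.

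SAP 19.2.1 has the table report the number and percentage of subjects with qualifying post-baseline results, by treatment group and parameter. A subject and parameter enter the listing "if at least one post-baseline value for that subject and parameter is markedly abnormal". The section then turns to the appendix listings for each panel, in which values outside the normal range are flagged, and says: "Local lab test results will only be presented in appendix data listings". No flag for the Appendix 3 criteria is described there.

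**The concern.** A single laboratory source suits by-visit means and shift tables, where one assay and one set of ranges keep visits comparable. The markedly abnormal table has a different purpose: it shows whether a subject ever crossed a predefined limit after baseline. Leaving recorded values out of such a count can only lower it.

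Safety is the first-named objective in SAP 3. Appendix 3 is the SAP's fixed laboratory criterion and does not depend on the investigator's judgement. A reader who wanted to know whether any local value met it would have to apply the criteria by hand to the appendix listings. Between-visit values may also be the short-lived ones: Protocol 3.1 has nutritional support reviewed at every visit and telephone contact, and Table 6-1 (footnote j) has adjustments take the safety laboratory data into account. An abnormality seen between visits may therefore be gone by the next central sample.

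**Working it through.** The plan gives no figure for this point, so there is nothing to reproduce. The check follows the rules to their result and then bounds the exposure from the documents.

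**What has to happen for a subject to be missed.** Take a local potassium above the Appendix 3 upper limit of 6.5 mmol/L in Week 13.
1. SAP 19.2 permits the local sample and records it in the eCRF.
2. The incidence table is one of the summaries, and the summaries use central results, so this value does not count.
3. The count is per subject and parameter. If any post-baseline central potassium for this subject is markedly abnormal, the subject is counted anyway.
4. The subject is therefore missed only if every markedly abnormal post-baseline value for that parameter is local. Resolving before the next central draw is necessary but not sufficient.

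**Occasions exposed** (Protocol Tables 6-1 to 6-4; the supplied protocol goes up to Amendment 2).
- Site weeks after baseline: 1, 2, 4, 6, 8, 10, 12, 15, 18, 21, 24, 28, which is 12.
- Phone weeks with optional laboratory tests: 3, 5, 7, 9, 11, 13, 14, 16, 17, 19, 20, 22, 23, which is 13 on treatment. Weeks 25, 26 and 27 make 16 to Week 28.
- At one draw per phone week there are at most 13 such occasions on treatment and 16 in all. The minimum is 0. SAP 19.2 sets no cap, so these are scheduled-week counts and not firm limits.

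**Nominal time to the next central draw.**
- 1 week: Weeks 3, 5, 7, 9, 11, 14, 17, 20, 23 (9 of 13).
- 2 weeks: Weeks 13, 16, 19, 22 (4 of 13).
- Follow-up: Week 25 has 3 weeks, Week 26 has 2, Week 27 has 1. To Week 28 the totals are 10, 5 and 1 of 16 for gaps of 1, 2 and 3 weeks.

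**Parameters exposed** (SAP Appendix 3).
- 18 chemistry + 5 hematology = 23 parameters.
- Table 6-1, footnote m, limits between-visit panels to chemistry and urinalysis. At most the 18 chemistry parameters are then exposed.
- Six are multiples of the upper limit of normal (ULN): alkaline phosphatase, ALT, AST, amylase, lipase and total bilirubin. The other 18 − 6 = 12 have absolute limits.

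**Effect of one missed subject on the reported percentage**, 100/n:
- Dose arm at the minimum of 10 (Protocol 4.1): 100/10 = 10 points.
- Standard of care group of 8 (the protocol's maximum): 100/8 = 12.5 points.
- Enrolment under the later amendment is not supplied. With assumed arms of 20 or 30: 100/20 = 5.0 and 100/30 = 3.3 points.

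These figures show how sensitive the table is to one subject. The documents do not give the number of local samples, so they do not estimate how many subjects are missed.

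**The case against.** The strongest reply is that this is a disclosed choice with a sound reason. One laboratory means one assay and one set of ranges, and six chemistry criteria depend on a ULN that the local form may not capture. If between-visit tests follow changes in parenteral support, as Protocol 6.1.6 and the table footnotes suggest, an arm with more changes is tested more often. A pooled count would then rise in that arm at equal risk per draw. This stands, and it is why the central-only table should remain the main summary.

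The loss may also be nil. Table 6-1, footnote m, describes home collection of between-visit samples with processing for the central laboratory, and such results would count. Against that, the SAP says: "This statistical analysis plan (SAP) is based on protocol amendment 4, dated 15 March 2016". That amendment is not supplied, and the SAP has a local-laboratory form, so local results are at least expected.

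Other safeguards exist. Clinically significant laboratory worsening is reported as an adverse event (Protocol 6.1.1.2 and 6.1.6), the DSMB reviews cumulative laboratory data (Protocol 4.5), and local values are listed. These limit the consequence but do not put the subject into the table, and the adverse event route rests on the investigator's judgement.

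A reader might infer two stronger points:
- **That the markedly abnormal listing is certainly central-only.** This is the likely reading, because the listing stands among the summaries and the appendix listings are introduced as additional outputs. But 19.2.1 does not say whether this listing is itself an appendix listing, and the shells are in a separate file (SAP Appendix 4), so it cannot be confirmed.
- **That the SAP contradicts itself.** SAP 8.3 says "All available data will be included in the safety analysis", and SAP 7.3 lets unscheduled measurements contribute to "the EOS/EOT value, or best/worst case value where applicable". The first sentence stands in the section on missing data and the second concerns unscheduled, not local, values. A specific source rule in 19.2 can govern both, so this is not a contradiction.

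**Conclusion.** The point holds for the incidence table. Following the SAP exactly, a subject whose only markedly abnormal values for a parameter are local is not counted, so this rule can understate the count and cannot overstate it. The size is unknown and may be zero. It depends on how often local laboratories were used under an amendment that is not supplied, and on values that never show as markedly abnormal at any central draw. Persistent abnormalities should be caught centrally.

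The documents do not support reading this as hidden safety data: the values are recorded and listed, and the clinically significant ones are reported as adverse events. Nor do they show a bias between arms. Unequal between-visit testing is possible, but nothing supplied shows that it occurs. The analysis is descriptive throughout (SAP 7.5), so no test or error rate is affected. The point is worth considering as a cheap improvement and does not challenge the study's conclusions.

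**What to change.** Keep the central-only incidence table as the main summary. Add one supplementary, source-flagged output (count and listing) that applies Appendix 3 to local as well as central post-baseline chemistry results, in SI units. Beside it, show the number of chemistry testing occasions per subject by arm and source. Use the reporting laboratory's ULN for the six ULN-based criteria where it was captured. Where it was not, limit the local part to the 12 criteria with absolute limits and say so. State in 19.2.1 that the markedly abnormal listing includes local values. A sentence in SAP 8.3 and 7.3 pointing to the source rule in 19.2 would help the reader but is optional.

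The cost is some SAP wording and one output from data that the SAP says are already in the eCRF. The absolute limits need at most unit conversion, and creatinine also needs age. Whether the local form holds units and ULN cannot be checked, so the standardisation effort is uncertain. The drawbacks are mixed laboratory sources and possibly unequal testing frequency between arms. The source flag, the retained central-only table and the row of testing occasions make both visible. If no local results exist, only the wording changes.
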